- We hypothesize that the combined administration of BCG and PANVAC™ may augment the BCG-induced cytotoxic T lymphocyte response against bladder cancer cells expressing MUC-1 and/or CEA and potentially reverse BCG failure in patients that have failed one induction course of BCG

Objectives:

- To determine if there is an improvement in disease-free survival (DFS*) with BCG + PANVAC compared with BCG alone in a phase II study in non-muscle invasive high-grade urothelial carcinoma of the bladder who have failed to respond to intravesical BCG.

*within 1 year post treatment

Eligibility:

- Individuals who have failed at least one previous induction course of intravesical BCG, defined as histologically confirmed persistent or relapsing tumor present on post-BCG endoscopic evaluation. All BCG failures will be considered for inclusion into the study, including BCG-refractory, -resistant, and -relapsing, as defined in the “Rationale and Background.” For the purposes of the study, “BCG-refractory” and “BCG-resistant” subjects will be considered to have “BCG-persistent” disease.
- Patients who are not currently candidates for radical cystectomy (e.g. patient refuses surgery, comorbidities preclude major surgery, etc.).
- Normal organ function, ECOG 0-2.

Design:

- This is a randomized, open label prospective, Phase II study in subjects with non-muscle invasive high grade urothelial carcinoma of the bladder who have failed at least one induction course of intravesical BCG, randomized to one of the following arms: TICE BCG +PANVACTTM or TICE BCG alone. Randomization is stratified by BCG treatment subgroup.
- All subjects will receive intravesical TICE BCG (50mg) as per usual standard of care once weekly (+/- 2 days) starting in week 3 for a total of 6 weeks.
- The combination arm will receive the pox viral vaccines that contain the transgenes for CEA and MUC-1 (both with modified HLA-A2 agonist epitopes) as well as 3 human T-cell costimulatory molecules, B7-1, ICAM-1, and LFA-3 [rV-PANVACTTM (vaccinia) and rF-PANVACTTM (fowlpox)] as follows:
 - rV-PANVACTTM 2 x 10⁸ pfu SQ at week 0 (+/- 7 days) only.
 - rF-PANVACTTM 1 x 10⁹ pfu SQ at weeks (+/- 7 days) 3, 7, 11, and 15.
- For this Phase II study, we will test the hypothesis that subjects in the TICE BCG +PANVACTTM arm have better disease-free survival than subjects in the TICE BCG alone arm.
- Patient accrual is targeted at one patient per month during the first 6 months and 1-2 patients every 1-2 months afterwards, and follow-up period after completing accrual will be 12 months post treatment.
- Based on a power of 84% and type 1 error (1-sided) of 0.15, a total of 49 subjects will need to be accrued.
- Allowing for a proportion of the subjects not being evaluable, a maximum of 54 subjects will be accrued.

SCHEMA

[figure not shown]

TABLE OF CONTENTS

PRÉCIS	2
SCHEMA	4
TABLE OF CONTENTS.....	5
1 OBJECTIVES	8
1.1 Primary Objective	8
1.2 Secondary Objectives.....	8
1.3 Exploratory Objectives	8
2 BACKGROUND	8
3 PATIENT SELECTION	11
3.1 Eligibility Criteria	11
3.2 Recruitment Strategies.....	14
3.3 Screening Evaluation	15
3.4 Baseline Evaluation	15
3.5 Accrual Estimates	16
4 REGISTRATION PROCEDURES	17
4.1 General Guidelines.....	17
4.2 Registration Procedures	17
4.3 Randomization Procedures	17
5 TREATMENT PLAN.....	18
5.1 Study Design.....	18
5.2 Trial Outline.....	19
5.3 Agent Administration.....	21
5.4 Dose Limiting Toxicity.....	22
5.5 General Concomitant Medication and Supportive Care Guidelines.....	24
5.6 Duration of Therapy.....	25
5.7 Duration of Follow Up.....	25
5.8 Criteria for Removal from Protocol Therapy and Off Study Criteria.....	25

6	DOSING DELAYS/DOSE MODIFICATIONS	27
6.1	TICE BCG	27
6.2	PANVACTM-V (vaccinia) and PANVACTM-F (fowlpox)	27
7	NIH REPORTING REQUIREMENTS / DATA AND SAFETY MONITORING PLAN	28
7.1	Definitions.....	28
7.2	OHSRP Office of Compliance and Training / IRB Reporting	29
7.3	NCI Clinical Director Reporting.....	29
7.4	NCI Guidance for Reporting Expedited Adverse Events for Multi-Center Trials	29
7.5	NIH Office of Science Policy (OSP)/Institutional Biosafety Committee (IBC) Reporting Criteria	30
7.6	NIH Required Data and Safety Monitoring Plan.....	31
8	ADVERSE EVENTS: LIST AND SPONSOR REPORTING REQUIREMENTS	31
8.1	Comprehensive Adverse Events and Potential Risks List(s) (CAEPRs).....	32
8.2	Definitions.....	38
8.3	Expedited Adverse Event Reporting to CTEP	39
8.4	Routine Adverse Event Reporting to CTEP	42
8.5	Secondary Malignancy.....	42
8.6	Second Malignancy.....	43
9	PHARMACEUTICAL INFORMATION.....	43
9.1	CTEP IND Agents	43
9.2	Commercial agent	59
10	BIOMARKER, CORRELATIVE, AND SPECIAL STUDIES	60
10.1	Laboratory Correlative Studies	60
10.2	Sample Storage, Tracking and Disposition.....	66
11	STUDY CALENDARS	68
12	MEASUREMENT OF EFFECT	73
12.1	Response Criteria	73

1 OBJECTIVES

1.1 PRIMARY OBJECTIVE

1.1.1 To determine if there is an improvement in disease-free survival (DFS*) with BCG + PANVAC compared with BCG alone in a phase II study in non-muscle invasive high-grade urothelial carcinoma of the bladder who have failed to respond to intravesical BCG. *within 1 year post treatment

1.2 SECONDARY OBJECTIVES

1.2.1 To estimate tumor upgrading and tumor upstaging rates for each study arm.
1.2.2 To determine the safety of the combination therapy.

1.3 EXPLORATORY OBJECTIVES

1.3.1 To assess the expression of CEA and MUC-1 antigens in bladder tumor specimens pre- and post-treatment in both arms
1.3.2 To assess the presence of CD4 and CD8 T cells in bladder tumor specimens pre- and post-treatment in both arms
1.3.3 To assess the presence of Tregs by double staining with FoxP3 and CD4 in bladder tumor specimens pre- and post-treatment in both arms
1.3.4 To assess the presence of myeloid derived suppressor cells (MDSC) in bladder tumor specimens pre- and post-treatment in both arms
1.3.5 To measure the CD4 antigen-specific response to CEA in peripheral blood mononuclear cells (PBMCs) obtained from blood
1.3.6 To measure the CD8 antigen-specific response to CEA, MUC-1, and Brachyury in all subjects who have the HLA-A2 allele in PBMCs obtained from blood
1.3.7 To analyze all PBMC samples by flow cytometry for the following cell types: CD4, CD8, Tregs, MDSCs, and Natural Killer (NK) cells
1.3.8 To analyze sera samples obtained from blood at all time points for antibodies to CEA, MUC-1, and Brachyury
1.3.9 To assess production of urinary cytokines and chemokines in collected samples

2 BACKGROUND

Bladder cancer accounts for the 4th most common cancer in men and the 12th most common cancer in women. An estimated 73,510 people living in the United States will be diagnosed with

bladder cancer in 2012, with approximately 14,880 dying of bladder cancer in the same year.¹ Most of these patients (>75%) will be diagnosed with non-muscle invasive bladder cancer and approximately 50% of these patients will present with high grade disease.² High grade non-muscle invasive bladder cancer (Ta, T1, and/or CIS) is difficult to treat because of high rates of recurrence and progression. The last major advance in bladder cancer therapy was the approval of bacillus Calmette-Guerin (BCG) in 1990 by the FDA.³ Currently, intravesical BCG given as an induction course (6 weeks of intravesical therapy) is the standard of care^{4,5} followed by maintenance therapy. BCG has an initial failure rate of ~35% in terms of disease recurrence or progression. In ~20-35% of cases that failed an initial induction course of BCG, a second course of induction BCG may be beneficial, but patients who fail two courses are often best served by radical cystectomy.⁶⁻⁸ Patients with CIS alone may respond at a higher rate to a second induction course, however, cystectomy may still be required in at least 1/3 of these patients. This surgery involves the en bloc removal of the bladder and adjacent organs (prostate in males and uterus in females) and concomitant creation of a urinary diversion, which can affect a patient's quality-of-life significantly. Moreover, Shabsigh et al. reported that 64% of patients who undergo cystectomy suffer at least one complication within the first 90 days after surgery⁹ and the operation has been reported to have at least a 2.5% perioperative mortality rate even at a high-volume center.¹⁰ This fact is reflected in a 2003 survey, which showed that 81% of urologists were reluctant to refer their patients to radical cystectomy despite failing 2 courses of intravesical therapy.¹¹ In summary, radical cystectomy has the potential for significant morbidity and therefore, an unmet clinical need for intravesical therapy exists for these high grade non-muscle invasive bladder cancers that fail BCG.

BCG failures can be subdivided into several groups based on the time to tumor response and/or recurrence.¹² BCG-refractory disease is defined as the inability to be disease-free by 6 months after an induction course of BCG. In contrast, BCG-resistant disease is defined as the inability to be disease-free by 3 months after an induction course of BCG. Finally, BCG-relapsing disease is defined as recurrence of disease after being disease-free for at least 6 months after receiving BCG therapy. Unfortunately, disease-free survival rates at 12 months are not as well-defined based on these subclassifications. Thus, clinical endpoint trials involving this population should be randomized and stratified according to these subgroups to help better predict responders to therapy.

BCG works by an unclear immunologic mechanism that promotes activation and infiltration of immune cells within the bladder wall. The immune system is critical as the administration of T cells to athymic animals has been shown to restore their ability to respond to BCG therapy.^{13,14} A hypothesized mechanism for BCG is that it induces macrophage cytotoxicity and that Th1 immune system cytokines (e.g. TNF- α , IFN- γ , IL-12, and IL-18) play a positive role in the macrophage cytotoxicity while Th2 immune system cytokines (e.g. IL-4, IL-10) and T regulatory cells (Tregs) are potentially inhibitory to this BCG-induced macrophage cytotoxicity.¹⁵ T cell infiltration appears important as the degree of infiltration (CD3, CD4, and CD8) has been shown to be significantly greater in patients with a complete response to BCG in comparison to patients with a partial response or treatment failure.¹⁶

Modulation of the immune system is one strategy employed in cancer therapeutics. Tumor associated antigens (TAAs), which are unique molecules minimally expressed by normal tissues and over-expressed in cancer cells, can be used as immunologic targets. Recently, researchers at

the NIH have developed a poxvirus cancer vaccine therapy called PANVAC™ that has demonstrated therapeutic efficacy against a variety of carcinomas. PANVAC™ consists of a primary vaccination with a replication competent recombinant vaccinia (rV-) viral vector followed by multiple booster vaccinations with a replication-incompetent recombinant fowlpox (rF-) viral vector. These vectors contain transgenes for both TAAs and human T cell co-stimulatory molecules. Although TAAs are weakly immunogenic, a method of disrupting immune tolerance is to introduce TAAs to the immune system through poxviral vectors.¹⁷ Antigen-specific active immunotherapy is designed to generate immune responses, particularly cell-mediated responses, against specific TAAs using vaccines that express one or more of these antigens.

The TAAs in PANVAC™ are epithelial mucin-1 (MUC-1) and carcinoembryonic antigen (CEA) which are altered and overexpressed in many cancers.¹⁸ MUC-1 is a glycosylated transmembrane protein that is overexpressed in almost all human carcinomas. Furthermore, it has been demonstrated that the c-terminus of MUC-1 functions as an oncogene.^{19,20} According to one study, MUC-1 is present in all cases of malignant urothelium, but increased expression is noted with higher grade and stage tumors.²¹ Another study demonstrated MUC-1 expression in 93% of bladder tumors studied.²² CEA is a glycosylated cell surface protein expressed in several tumors as well and in particularly in colorectal, ovarian, bladder, breast, and gastric tumors.²³ CEA is expressed in 76% of high grade tumors and in 59% of pT1 bladder tumors.²⁴

Co-stimulatory molecules are critical in the generation of T-cell responses especially against weak antigens such as TAAs. The initiation of an immune response requires at least two signals for activation of naïve T cells by antigen-presenting cells. The first signal is antigen specific, delivered through the T-cell receptor via the peptide/MHC, and causes the T cell to enter the cell cycle. The second, “co-stimulatory,” signal is required for cytokine production and proliferation. At least three distinct molecules normally found on the surface of professional antigen-presenting cells have been reported to be capable of providing the second signal critical for T-cell activation: B7-1, ICAM-1, and LFA-3. Both antigen and co-stimulatory molecules must be expressed in the same cell to properly engage the TCR and co-stimulatory receptor. In order to achieve this, multigene constructs using poxviral vectors (avipox and vaccinia) have been generated. The co-stimulatory molecules are B7.1 (CD80), ICAM01 (CD54), and LFA-3 (CD58) and are referred to as TRICOM (triad of co-stimulatory molecules).²⁵ Each of these co-stimulatory molecules binds to a different ligand, and the second messenger pathways of each ligand are unique, raising the potential for synergy of these molecules. The vaccines are therefore, summarized as rV-CEA-MUC-1-TRICOM (rV-PANVAC™) and rF-CEA-MUC-1-TRICOM (rF-PANVAC™).

PANVAC™ is injected subcutaneously, processed by antigen-presenting cells (APCs), and then induces CEA- and MUC-1-specific cytotoxic T lymphocyte responses that are then potentiated by the co-stimulatory molecules. The pox viral vectors have a high rate of cellular infection, can carry large amounts of transgenes, process genes in the cytoplasm of infected cells with a low risk of incorporation within the host genome, and have an established history of clinical safety in patients. In fact, several hundred patients have already been treated on clinical trials with pox viral vectors and there have been no dose limiting toxicities attributable to these vaccines.¹⁸

Initial studies with PANVAC showed that it was well tolerated and was associated with objective responses in some patients. One patient with metastatic ovarian cancer and symptomatic ascites had complete resolution of her ascites and normalization of her CA-125 (from 300 to <20) for 18 months.²⁶ A patient with metastatic breast cancer has an ongoing complete response of her disease for over 3 years.²⁷ The final results of a randomized phase II study were recently reported. This study enrolled 48 patients with metastatic breast cancer and randomized them to weekly docetaxel with PANVAC monthly vs. docetaxel alone. The primary endpoint was PFS. The median PFS for patients randomized to the combination arm was 6.6 months vs. 3.8 months in the chemotherapy alone arm.²⁸

A phase II randomized controlled study involved 74 patients with completely resected metastases from colorectal cancer, who had received perioperative chemotherapy.²⁹ Patients were randomized to receive 4 vaccinations with either PANVAC or dendritic cells modified with PANVAC. There was no significant difference in 2-year recurrence-free survival among the DC arm (50%), the PANVAC arm (56%), and a contemporary control arm (55%). However, at a median follow-up of 40 months, the survival rate for vaccinated patients was 81%, which far exceeded that of the unvaccinated controls.

Recently, a PSA specific vaccine, rV-PSA TRICOM and rF-PSA-TRICOM, was evaluated in a randomized, placebo-controlled, blinded Phase II study for minimally symptomatic metastatic castration-resistant prostate cancer. Although no difference in progression free survival was noted, patients receiving the vaccine had longer median survival by 8.5 months with hazard ratio of 0.56 (95% CI, 0.37 to 0.85), p=0.0061.³⁰ Other studies have demonstrated safety of the vaccine in solid organ tumors when administered subcutaneously.^{18,26,27} These initial studies suggest safety and activity in a broad range of tumor types.

High grade non-muscle invasive bladder cancer tends to respond well to BCG and when it does not, there is evidence to suggest an incomplete or inefficient immune response. Given that CEA and MUC-1 are overexpressed in bladder cancer, we hypothesize that PANVAC™ will augment the BCG-induced cytotoxic T lymphocyte response against bladder cancer cells expressing MUC-1 and/or CEA, which will clinically result in a greater disease-free survival rate than BCG alone in patients who have failed at least one previous course of intravesical BCG. We also hypothesize that the PANVAC+BCG group will demonstrate decreased tumor upgrading and tumor upstaging, particularly with regards to invasion of the detrusor musculature, and predict that the combination treatment will not demonstrate greater treatment-related toxicities to intravesical BCG alone. Finally, we hypothesize that the immune response will be augmented in the PANVAC+BCG group compared to BCG alone as measured by secondary immunologic correlates described below.

3 PATIENT SELECTION

3.1 ELIGIBILITY CRITERIA

3.1.1 Inclusion Criteria

- 3.1.1.1 Patients must have histologically confirmed localized high grade (G3) transitional cell carcinoma (urothelial carcinoma) of the bladder that is stage Ta, T1, and/or CIS

confirmed by the Laboratory of Pathology, NCI 90 days prior to study entry. This can be obtained at an outside hospital prior to entry into the study or at the NCI. However, all outside pathology specimens will require that the formalin-fixed paraffin embedded tissues be re-read by the Laboratory of Pathology, NCI. For patients enrolled at collaborating trial sites, diagnosis must be confirmed by the Department of Pathology at the institution where the patient is enrolled on the trial. Pathology can also be reviewed by the Laboratory of Pathology at the NCI if the participating trial site prefers another pathologic evaluation.

- 3.1.1.2 Patients have failed at least one previous induction course of intravesical BCG, defined as histologically confirmed persistent or relapsing tumor present on post-BCG endoscopic evaluation. All BCG failures will be considered for inclusion into the study, including BCG-refractory, -resistant, and -relapsing, as defined in the “Rationale and Background.” For the purposes of the study, “BCG-refractory” and “BCG-resistant” subjects will be considered to have “BCG-persistent” disease.
- 3.1.1.3 Patients who are not currently candidates for radical cystectomy (e.g. patient refuses surgery, comorbidities preclude major surgery, etc.).
- 3.1.1.4 Age ≥ 18 years.

Because no dosing or adverse event data are currently available on the use of BCG in combination with PANVAC™ in patients <18 years of age, children are excluded from this study.

- 3.1.1.5 ECOG performance status ≤ 2 (see Appendix A, Section 17.1).

- 3.1.1.6 Patients must have normal organ and marrow function as defined below:

- absolute neutrophil count	$\geq 1,500/\text{mcL}$
- platelets	$\geq 50,000/\text{mcL}$
- total bilirubin	$\leq 1.5 \times$ institutional upper limit of normal
- AST(SGOT)/ALT(SGPT)	$\leq 3 \times$ institutional upper limit of normal
- estimated GFR (calculated using CKD-EPI equation)	$\geq 30 \text{ mL/min}/1.73 \text{ sq.m.}$

- 3.1.1.7 Computerized Tomography (CT) urogram or Magnetic Resonance Imaging (MRI) urogram. If urogram protocol not available or contrast allergy/poor renal function preclude such imaging, then noncontrast CT or MRI of the abdomen/pelvis within 45 days of study entry will suffice.
- 3.1.1.8 Chest x-ray negative for metastatic disease.
- 3.1.1.9 Ability of patient to understand and the willingness to sign a written informed consent document.

3.1.2 Exclusion Criteria

- 3.1.2.1 Previous pelvic radiation for bladder or prostate cancer if performed <12 months prior to enrollment into the study.
- 3.1.2.2 Patients who are receiving any other concurrent investigational agents (patients are eligible to enroll 4 weeks after completion of prior agent).
- 3.1.2.3 Patients who have had chemotherapy within 4 weeks (6 weeks for nitrosoureas or mitomycin C) prior to entering the study or those who have not recovered from adverse events due to agents administered more than 4 weeks earlier. There will be at least a 3 week delay from the time of a previous bladder biopsy/TURBT to allow for adequate bladder healing prior to enrollment.
- 3.1.2.4 Patients with a history of encephalitis, multiple sclerosis, or seizures within the last year (from seizure disorder or brain metastasis) should be excluded from this clinical trial because of their poor prognosis and because they often develop progressive neurologic dysfunction that would confound the evaluation of neurologic and other adverse events.
- 3.1.2.5 History of allergy or untoward reaction to prior vaccination with vaccinia virus
- 3.1.2.6 Patients should have no evidence of being immunocompromised as listed below:
 - Human immunodeficiency virus positivity due to the potential for decreased tolerance and risk for severe side effects
 - Active autoimmune diseases requiring treatment or a history of autoimmune disease that might be stimulated by vaccine treatment. This requirement is due to the potential risks of exacerbating autoimmunity. Patients with endocrine disease that is controlled by replacement therapy including thyroid disease and adrenal disease and vitiligo may be enrolled.
 - History of splenectomy
- 3.1.2.7 Uncontrolled intercurrent illness which would interfere with the ability of the patient to carry out the treatment program, including, but not limited to, active second malignancy other than a cancer that has been successfully treated resulting in a high likelihood of long-term survival (e.g. completely resected basal cell or squamous cell carcinoma of the skin, stage 1 renal cell carcinoma treated with partial nephrectomy, treated low risk prostate cancer, etc.), inflammatory bowel disease (e.g. Crohn's disease or ulcerative colitis), active diverticulitis, ongoing or active infection, symptomatic congestive heart failure, unstable angina pectoris, cardiac arrhythmia, or psychiatric illness/social situations that would limit compliance with study requirements.
- 3.1.2.8 Pregnant women are excluded from this study because the vaccines used in the study

may have the potential for teratogenic or abortifacient effects. Because there is an unknown but potential risk for adverse events in nursing infants secondary to treatment of the mother with the vaccine, breastfeeding should be discontinued if the mother is treated with vaccines. These potential risks may also apply to other agents used in this study. Patients must agree to use adequate contraception (hormonal or barrier method of birth control; abstinence) prior to study entry and for the duration of study participation. Should a woman become pregnant or suspect she is pregnant while her partner is participating in this study, she should inform her treating physician immediately

- 3.1.2.9 Concurrent use of systemic steroids, except for physiologic doses of systemic steroids for replacement or local (topical, nasal, or inhaled) steroid use. Limited doses of systemic steroids to prevent IV contrast, allergic reaction, or anaphylaxis (in patients who have known contrast allergies) are allowed. Although topical steroids are allowed, steroid eye-drops are contraindicated
- 3.1.2.10 Altered immune function, including immunodeficiency or history of immunodeficiency; eczema; history of eczema, or other eczematoid skin disorders; or those with acute, chronic or exfoliative skin conditions (e.g. atopic dermatitis, burns, impetigo, varicella zoster, severe acne, or other open rashes or wounds). There is an increased risk to patients or contacts with eczema, atopic dermatitis, and other immune deficiencies who are at risk for eczema vaccination.
- 3.1.2.11 Medical conditions which, in the opinion of the investigators, would jeopardize the patient or the integrity of the data obtained
- 3.1.2.12 Serious hypersensitivity reaction to egg products
- 3.1.2.13 Chronic hepatitis infection, including B and C, because of potential immune impairment
- 3.1.2.14 Clinically significant cardiomyopathy or cardiac complications, including recent myocardial infarction or cerebrovascular accident within one year, and/or unstable or uncontrolled angina
- 3.1.2.15 Previous intolerance to BCG intravesical therapy suggested by development of systemic BCG infection in the past and/or grade 4 or greater adverse effect by CTCAE v5.0.
- 3.1.2.16 Patients unable to avoid close contact or household contact with the following high-risk individuals for three weeks after the Day 1 vaccination: (a) children \leq 3 years of age, (b) pregnant or nursing women, (c) individuals with prior or concurrent extensive eczema or other eczematoid skin disorders, or (d) immunocompromised individuals, such as those with HIV.

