4.2 REGISTRATION PROCEDURES

4.2.1 Registration at the CCR

Authorized staff must register an eligible candidate with NCI Central Registration Office (CRO) within 24 hours of signing consent. A registration Eligibility Checklist from the web site (<http://home.ccr.cancer.gov/intra/eligibility/welcome.htm>) must be completed and sent via encrypted email to: NCI Central Registration Office [contact].

After confirmation of eligibility at Central Registration Office, CRO staff will call pharmacy to advise them of the acceptance of the patient on the protocol prior to the release of any investigational agents. Verification of Registration will be forwarded electronically via e-mail to the research team. A recorder is available during non-working hours.

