4.2.2 Participating Site Registration

Registration will be a two part process as patients are screened on this protocol. A protocol registration form will be supplied by the CCR study coordinator and updates will be provided as needed. Subject eligibility and demographic information is required for registration. To initially register a subject, after the participant has signed consent, complete the top portion of the form and send to CCR study coordinator. Once eligibility is confirmed, after completion of screening studies, complete the remainder of the form which is the eligibility checklist, indicating that the patient is being registered for treatment and send to CCR study coordinator. In addition, source documents supporting the eligibility criteria must be sent to the CCR study coordinator. The CCR study coordinator will notify you either by e-mail or fax that the protocol registration form has been received which will include the unique patient/subject ID number. Questions about eligibility should be directed to the CCR study coordinator or PI. Questions related to registration should be directed to the CCR study coordinator.

Subjects that do not meet screening criteria should be removed from the study following the procedure in section [5.8.3](#).

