4.3 RANDOMIZATION PROCEDURES

There are two arms to this study and subjects will be randomized equally to either the TICE BCG arm or the combination arm of TICE BCG + PANVAC™. The study arms are described in detail below in Section [5.1](#). The arms will be stratified during randomization for TICE BCG

subgroup based on number of previous induction courses and time of recurrence. This is described in more detail along with the statistical analysis in the statistical section (Section 14).

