- has a moderate or severe acute illness, until the illness resolves.
- is undergoing topical steroid therapy for inflammatory eye diseases, or undergoing therapy with systemic steroids; potential immune suppression increases risk for vaccinia-related complications.
- At this time, until a more definitive causal relationship is determined, it is recommended that patients with known CHF or clinically significant cardiomyopathy, not be vaccinated with recombinant vaccinia-based vaccines, due to the potential for development of myocarditis and/or pericarditis.

Although the CDC believes that there is no evidence to conclude that the licensed vaccinia vaccine used in the Smallpox Vaccination Program caused angina or heart attacks, it acknowledges a possible causal relationship between the vaccination and heart inflammation. The CDC continues to study the relationship, but in the meantime, recommends excluding individuals with underlying heart disease from participation in the current Smallpox Vaccination Program. Patients are being immunized with recombinant vaccinia vaccines with therapeutic intent and will be evaluated for cardiovascular risk factors and recent or symptomatic cardiac events per protocol eligibility criteria. Patients will be encouraged to minimize cardiovascular disease risks and encouraged to follow risk reduction according to standard medical practice.

Due to the method of manufacturing (virus grown in primary chicken embryo dermal cells), do not administer the recombinant vaccinia vaccine to patients with a history of allergy to eggs or egg products. Do not administer the recombinant vaccinia vaccine to patients with a history of allergy or serious reaction to prior vaccinia vaccination (e.g., smallpox vaccination).

Potential Complications Associated With Recombinant Vaccinia Vaccination

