- Biosafety in Microbiological and Biomedical Laboratories; U. S. Department of Health and Human Services Centers for Disease Control and Prevention and National Institutes of Health. See current edition at:
<http://www.cdc.gov/biosafety/publications/index.htm>

Patient Care Implications

Cover vaccination sites with a sterile dry dressing (e.g., Telfa pad). Once the injection site is healed, no further barrier is necessary. As a precaution, protect injection sites that are exhibiting evidence of weeping, oozing or ulceration with a sterile dry dressing. In these circumstances, instruct patients to avoid direct contact of the injection site with susceptible individuals (e.g.; those who may be immunocompromised by disease or therapy). Instruct patients to avoid becoming pregnant, breast feeding or fathering a child for at least 4 months following therapy

completion with the recombinant vaccine. Instruct patients receiving fowlpox vaccines to avoid direct contact with pet birds for at least 72 hours after vaccination or while there are any visible lesions at the injection site.

Due to the method of manufacturing (virus grown in primary chicken embryo dermal cells), patients with a history of allergy to eggs or egg products should not receive the vaccine.

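### The egg-allergy exclusion is narrower than the contraindication in Section 9, so a candidate with a non-serious egg allergy meets the listed criteria and can be randomised to PANVAC (minor)

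*Combined protocol and SAP*

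**What the plan says.** Three places in the combined protocol and SAP deal with egg allergy.

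- Section 3.1.2, criterion 3.1.2.12, excludes a candidate with a "Serious hypersensitivity reaction to egg products".
- Section 9.1.1, on the vaccinia vector PANVAC-V, tells staff: "do not administer the recombinant vaccinia vaccine to patients with a history of allergy to eggs or egg products".
- Section 9.1.2, on the fowlpox vector PANVAC-F, says that "patients with a history of allergy to eggs or egg products should not receive the vaccine".

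Both Section 9 statements give the same reason, that the virus is grown in chicken embryo cells. No other eligibility criterion, screening or baseline item, or dosing-delay rule names egg allergy.

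Two neighbouring criteria matter. Criterion 3.1.2.5 excludes a "History of allergy or untoward reaction to prior vaccination with vaccinia virus", with no severity threshold. Criterion 3.1.2.11 is a general discretionary exclusion: "Medical conditions which, in the opinion of the investigators, would jeopardize the patient or the integrity of the data obtained".

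Section 4.3 states that "subjects will be randomized equally to either the TICE BCG arm or the combination arm".

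**The concern.** An eligibility list should remove, before allocation, anyone who cannot safely receive either arm. Here the list and the product information disagree about who that is. A candidate whose egg allergy has never caused a serious reaction is acceptable under 3.1.2.12 but should not receive either vector under Section 9.

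Two things are at stake for such a patient in the combination arm. If the Section 9 text is missed, the patient receives a vaccine that the protocol contraindicates. If it is followed, the patient has been randomised to a treatment that cannot be given and remains in the PANVAC arm on BCG alone. Section 14.4.2 keeps eligible patients in the main analysis, with a possible exception for those who received no study medication. Since both arms receive BCG, that exception would not clearly apply.

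**Working it through.** The plan states no figure on this point, so the check compares texts and adds one count from the treatment schedule.

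**Who is barred, text by text**

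| History | 3.1.2.12 | 9.1.1 (PANVAC-V) | 9.1.2 (PANVAC-F) |
|---|---|---|---|
| Serious reaction to egg products | Excluded | Do not give | Should not receive |
| Non-serious egg allergy | Not excluded | Do not give | Should not receive |
| No egg allergy | Not excluded | No bar | No bar |

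The texts differ only in the middle row.

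**Is the missing qualifier in Section 9 just loose wording?** The next sentence of 9.1.1, on prior vaccinia vaccination, bars an allergy or a serious reaction. That text does use a severity word where one is wanted, and it uses none for egg allergy. The protocol gives no reason for the narrower wording in 3.1.2.12.

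**Path of a candidate in the middle row**

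1. Under 5.2.1, a candidate who meets the entry criteria is enrolled.
2. Allocation is equal (4.3), so the chance of the combination arm is 1/2.
3. Sections 5.2.3.2 and 5.2.3.4 schedule the vaccine for everyone in that arm, with no egg-allergy exception.
4. Injections scheduled (5.1.2): one vaccinia dose at week 0, plus fowlpox doses at weeks 3, 7, 11 and 15. That is 1 + 4 = 5, all covered by the Section 9 statements.

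**What could stop this**

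- *Criterion 3.1.2.11.* It acts before randomisation, but it depends on the investigator's opinion and does not name egg allergy.
- *Section 9 read at screening.* This also acts before randomisation if it happens. History is taken at screening (3.3.1.1), but nothing there sends the investigator to the Section 9 egg statements.
- *Central registration.* Section 4.2.1 says "After confirmation of eligibility at Central Registration Office, CRO staff will call pharmacy", and 4.2.2 says that "source documents supporting the eligibility criteria must be sent to the CCR study coordinator". Both confirm eligibility. The checklist itself is not reproduced, so its egg wording cannot be verified. If it follows 3.1.2.12, it passes this candidate.
- *Section 5.3.3.* It sends staff to Section 9 before dosing, for safe handling and disposal. The egg statements sit in the patient-care text, and this step comes after allocation.

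None of these makes exclusion mandatory before randomisation for a non-serious egg allergy.

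**Number affected.** The documents give no prevalence of egg allergy and no count of such patients. No number is derived, and no power calculation is made.

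**The case against.** The best reply is that Section 9 belongs to the same protocol and gives a plain instruction not to vaccinate, so harm requires staff to breach it. Section 9 is also available at screening. An investigator who finds an egg allergy can use 3.1.2.11, and 4.2.2 directs eligibility questions to the coordinator or principal investigator. It would be wrong to say that every safeguard acts only after allocation. That much stands. It makes exposure less likely, but it leaves the outcome to individual judgement, and following Section 9 only at dosing still leaves an unvaccinated patient in the PANVAC arm.

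The comparison with 3.1.2.5 carries limited weight. That criterion refers to any untoward reaction, whereas 9.1.1 refers to a serious one, so the eligibility list was not simply copied from Section 9. The contrast does not prove that the egg wording was a slip.

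Timing is the other strong reply. Section 3.5 projected primary completion for December 2017. Section 8 says the study closed with CTEP, which supplied the vaccine, on 1 May 2019. New vaccination looks unlikely, although the documents do not state whether accrual has ended.

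**Conclusion.** The inconsistency is real and can be read directly from the text. A candidate with a non-serious egg allergy meets the listed criteria and has a 1 in 2 chance of an arm with five scheduled injections that Section 9 contraindicates. This assumes that the investigator neither uses 3.1.2.11 nor acts on Section 9 at screening. The number of such patients is unknown and may be zero. No endpoint, analysis or sample-size figure is affected. Severity is minor.

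Two stronger readings are not supported.

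- A reader might halve the five injections and call 2.5 the expected number of contraindicated doses per enrolled egg-allergic patient. That assumes Section 9 is ignored at every visit. If it is followed, the number is zero, and 6.2.1 stops further vaccination after certain allergic or grade 4 toxicities. Five is the number scheduled, and so a ceiling.
- A reader might infer the same gap for congestive heart failure, because 3.1.2.7 names only symptomatic disease. However, the myocarditis text in 9.1.1 itself makes known heart failure a ground for ineligibility where the listed criteria have not already excluded the patient. The list in 3.1.2.7 is open-ended, and 3.1.2.14 covers cardiac complications. That question is largely dealt with.

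**What to change.** Reword 3.1.2.12 to exclude any history of allergy to eggs or egg products, matching 9.1.1 and 9.1.2. Make sure the eligibility checklist carries the same wording, and apply it to all candidates before randomisation, whichever arm they might receive.

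The cost is one line in the protocol and, if needed, one on the checklist. No new test is required, because history is already taken at screening. The downside is that a few candidates would be screened out.

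If enrolment has ended, check the recorded histories of PANVAC-arm patients against the wider wording and report any egg-allergic patient who was vaccinated. The cost is then a review of existing records.
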